**If yes, please specify and briefly explain:**

Click or tap here to enter text.

**Describe any equipment to be used on the subjects, calibration procedures, & safety checks.**

- **Computer vision syndrome questionnaire (CVS-Q)** is a reliable and valid tool for measuring frequency and intensity of visual symptoms related to computer use in the workplace.
- **Binocular logMar (H/Lo contrast) visual acuity at 6M and 40cm.** The M&S Technologies Smart System II (M&S Technologies, Niles, IL) has been shown to be comparable to ETDRS and Pelli Robson charts. Computer tests have been shown to a reliable, capable way of assessing vision.
- **Binocular range of clear vision.** Use a near card with subject observing an isolated 20/30 target on the phoropter near testing rod. Pull back until subject report blur (repeat 3 times). Push in until subject report blur (repeat 3 times).
- **Subjective assessment of accommodation** is assessed by plotting a binocular defocus curve over-refraction at 6M (-3.00 to +3.00D in 0.50D steps) in phoropter while wearing contact lenses. Room luminance will be controlled and subjects will view optotypes through a standardized 4 mm aperture to reduce confounding effects on retinal defocus. Lenses will be presented in a randomized order.
- **Objective assessment of accommodation** Multiple studies support quantitative and qualitative changes in accommodation may be associated with asthenopia. The Grand Seiko WR 5500 (AIT, Bensenville, IL) has been shown to be capable of reliably measuring objective accommodation.

**Identify all personnel who will be collecting data from subjects or operating equipment and their special skills or qualifications. (Add extra pages if needed.)**

[name]

## Application for Initial SCO IRB Review: Protocols Involving Human Subjects

Does the project require the use of hazardous materials, such as radioactive substances or biological tissues (human or animal)? ☐Yes ☒No

If yes, what precautions will be taken for handling and storing these materials?

Click or tap here to enter text.

[Click here to see a list of items that must be included in the protocol to be turned in with this application.](#)

## Application for Initial SCO IRB Review: Protocols Involving Human Subjects

Informed consent containing the basic elements and applicable additional elements as outlined in the SCO IRB document "Elements of Informed Consent" must be obtained from subjects BEFORE participation in any study. However, if ALL of the necessary criteria are met, you may apply for permission to alter some or all of the elements or to have the informed consent requirement waived altogether. Click the button to the left to see the criteria necessary to waive or alter the IC:

Criteria for waiver/alteration IC

If you wish to apply for a WAIVER or ALTERATION of the informed consent document and process, specify whether you are requesting a waiver or an alteration and give the rationale below:

Click or tap here to enter text.

If you plan to obtain informed consent, but wish to waive DOCUMENTATION of informed consent, give your rationale below:

Click or tap here to enter text.

List the TOTAL number of subjects AT SCO that you wish to enroll: 30

Is this a MULTI-CENTER study? ☐ Yes ☒ No

If yes, list the TOTAL enrollment at all sites: Click or tap here to enter text.

Will the GENDER or RACE of the subjects be limited? ☐ Yes ☒ No

If yes, give rationale: Click or tap here to enter text.

Check each of the populations below that will be used in your research:

- |   |  |   |
|---|--|---|
|  Adults with cognitive impairment |  Patients                                |  SCO or TEC employees |
|  Pregnant women or neonates       |  SCO students                 |  Other                |
|  Prisoners                        |  Minors (<18 yrs)                        |   |
|  Non English-speaking subjects    |  Anyone likely to need surrogate consent |   |

Check all of the following subject recruitment methods that will be used. You will also need to ATTACH a copy of all printed ads, text-based messages, scripts of announcements and voice/verbal recruitment messages, etc.

- |  |   |                                    |
|--|---|------------------------------------|
|  Flyers, banners, or other postings            |  Email |  Telephone |
|  Public announcements before groups            |  Text msg         |  US mail   |
|  Radio or TV ads                               |  Social Media     |                                    |
|  Recruitment by clinicians or staff |  Other            | Click or tap here to enter text.   |

## Background and Rationale:

Computers, tablets, smartphones, and other digital devices have become an integral part of daily life. The average daily screen time now exceeds seven hours per day, a number that continues to rise amid growing reliance on remote work, virtual education, and streaming media platforms. As screen time continues to escalate, an increasing number of individuals are reporting symptoms associated with prolonged digital usage. This condition, referred to as Computer Vision Syndrome (CVS) or digital eye strain, encompasses a spectrum of visual and ocular symptoms including eye fatigue, dryness, blurred vision, and headaches.

A systematic review found that the prevalence of CVS among digital device users varies widely, from 38.6% to 95.8%, depending on the criteria used and the population studied. The etiology of CVS is multifactorial and can be divided into three broad categories: refractive and accommodative demand, binocular vision stress, and dry eye, often exacerbated by reduced blink rates during screen use. Contact lens wearers, in particular, may face heightened risks as lens wear can amplify dry eye symptoms during digital device use, stressing the importance of tailored lens designs.

In response to these challenges, the contact lens industry has developed new lens technologies aimed at mitigating the visual strain associated with digital screen use. Innovations include designs that incorporate blue light filtering technology, reduce accommodative demand, and promote tear film stability. Despite these advances, the current body of evidence evaluating the clinical efficacy of such lenses is limited, and heterogeneity in materials, optical profiles, and individual wearer characteristics presents further challenges to generalizability.

Given the increasing digital dependency and the rising public health impact of CVS, there is a critical need for rigorous, evidence-based research to assess the performance of emerging contact lens technologies. The proposed study will address this gap by comparing the efficacy of two novel *stenfilcon A* contact lens designs in alleviating accommodative burden associated with digital device usage.

### Experimental design:

This is a randomized, double-masked, crossover clinical trial. Subjects (N= 30) will be randomly assigned to wear either the MyDay (stenfilcon A, Scottsville, NY) and then the MyDay Energys (stenfilcon A, Scottsville, NY) single vision contact lenses for a period of 5 days. Subjects will then be crossed over to the opposing design after a three-day wash-out period.

Symptoms and visual performance will be assessed at baseline and exit from each design using primary outcomes measures.

- **Computer vision syndrome questionnaire (CVS-Q)** is a reliable and valid tool for measuring frequency and intensity of visual symptoms related to computer use in the workplace.
- **Binocular logMar (H/Lo contrast) visual acuity at 6M and 40cm.** The M&S Technologies Smart System II (M&S Technologies, Niles, IL) has been shown to be comparable to ETDRS and Pelli Robson charts. Computer tests have been shown to a reliable, capable way of assessing vision.
- **Binocular range of clear vision.** Use a near card with subject observing an isolated 20/30 target on the phoropter near testing rod. Pull back until subject report blur (repeat 3 times). Push in until subject report blur (repeat 3 times).
- **Subjective assessment of accommodation** is assessed by plotting a binocular defocus curve over-refraction at 6M (-3.00 to +3.00D in 0.50D steps) in phoropter while wearing contact lenses. Room luminance will be controlled and subjects will view optotypes through a standardized 4 mm aperture to reduce confounding effects on retinal defocus. Lenses will be presented in a randomized order.
- **Objective assessment of accommodation** Multiple studies support quantitative and qualitative changes in accommodation may be associated with asthenopia. The Grand Seiko WR 5500 (AIT, Bensenville, IL) has been shown to be capable of reliably measuring objective accommodation.

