### *Exclusion criteria:*

- Monovision
- History of refractive surgery
- Binocular vision abnormalities
- Current ocular or systemic disease that may affect the eye
- Allergic reactions of ocular surfaces or adnexa that may be induced or exaggerated by wearing contact lenses or use of contact lens solutions.

- If eyes become red or irritated.
- The patient is unable to follow lens care regimen or unable to obtain assistance to do so

*Sample size:*

Sample size calculations were based on logMAR visual acuity values from Elliott et al. (1995). Assuming a clinically significant difference of 0.1 logMAR and a standard deviation of 0.06, a two-tailed t-test with  $\alpha=0.05$  and  $\beta=0.20$  indicates a sample size of <27 subjects. To account for a 10% dropout rate, 30 subjects will be enrolled.

*Statistical Analysis:*

Descriptive statistics will be provided for the cohort including age, gender, equivalent spherical refraction, hours spent using a smart device per day, and average wearing time per day. Primary outcome measures will be compared using either parametric or non-parametric testing after testing sample distributions for normalcy. Correlations between CVS-Q and outcome measures will be assessed.

This study will comply with the tenets of the Helsinki Declarations and will be approved by the Institutional Review Board.

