## C. Statement of Research Plan

### a. Statement of Problem:

Computer Vision Syndrome (CVS), also referred to as digital eye strain, is a group of vision-related issues arising from prolonged digital screen use. According to the American Optometric Association, many individuals experience discomfort that increases with extended screen exposure. With widespread use of digital devices across all age groups, individuals spend over five hours per day on screens, exacerbating CVS symptoms.

Contact lens manufacturers continue to develop designs aimed at mitigating CVS symptoms by reducing higher-order aberrations, accommodative/convergence demands, and improving tear film stability. However, comparative studies evaluating these claims are limited due to variability in lens properties. This study aims to assess the validity of these claims by comparing symptoms and visual performance of two novel stenfilcon A lens designs.

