**c. Institutional and other resources available:**

All patient visits will be conducted at the Southern College of Optometry (SCO). The M&S Technologies Smart System II needed for binocular visual acuity testing and subjective assessment of accommodation, in addition to the Grand Seiko WR 5500 needed for objective assessment of accommodation, will also be

provided by the Southern College of Optometry. The study contact lenses will be provided by CooperVision. Funding for student research participation and conference travel is supported by the SCO Summer Research Fellowship Program.

- d. **Relevance of Problem to Optometry or Vision Science:** Computers, tablets, e-readers, and cell phones garner an ever-increasing presence in patients' day-to-day lives. Optometrists and vision scientists are likely to be confronted with increasing levels of Computer Vision Syndrome in patient care. Research on the impact of contact lens designs on CVS symptoms is essential for guiding clinical recommendations. This study will contribute valuable data regarding the efficacy of novel lenses like Biofinity Energys and MyDay Energys in alleviating CVS.
- e. **Plans for Publication:** An abstract describing the primary outcome will be submitted to Academy 2026 Anaheim, and a manuscript on the same topic will be submitted to Contact Lens & Anterior Eye.

f. **Time Table:**

	2025	2025	2025	2025	2025	2026
	April	May	June	July	Aug	May
Activity						
IRB Preparation						
Data Collection						
Data Analysis						
Final Study Report						

D. **Budget**

Projected Expenses	Cost per unit	Units	Total	Source of funding
Research Subject Compensation	\$50 (3 visits)	30 subjects	1500	
Statistician (\$125/hour)	\$125/hour	2 hours	250	
Fluorescein Strips	\$80	1 box	80	
Contact lens cases	0.21/each	90	19	
		Total	\$1849	BSK grant

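### All five listed measures are called primary, with no ranking and no multiplicity control, so the plan has no single identifiable confirmatory test

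*Combined protocol and SAP*

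**What the plan says.** The protocol's Experimental design section introduces its outcomes with: "Symptoms and visual performance will be assessed at baseline and exit from each design using primary outcomes measures". Five bullets follow, all under that label:

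- "Computer vision syndrome questionnaire (CVS-Q"), a symptom score;
- "Binocular logMar (H/Lo contrast) visual acuity at 6M and 40cm", which is two contrasts at two distances;
- binocular range of clear vision: "Pull back until subject report blur (repeat 3 times). Push in until subject report blur (repeat 3 times");
- subjective accommodation from a "defocus curve over-refraction at 6M (-3.00 to +3.00D in 0.50D steps");
- objective accommodation by autorefractor, with no parameter or number of stimulus levels given.

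The Statistical Analysis paragraph says: "Primary outcome measures will be compared using either parametric or non-parametric testing after testing sample distributions for normalcy". It adds correlations between the CVS-Q and the other measures. It gives no order of importance, secondary tier, gatekeeping or adjustment.

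The research plan in the funding application (section C.b) has the same structure and the same statistical text, but its list omits range of clear vision. Section C.e plans an abstract and a manuscript on one primary outcome without saying which. The sample size is based on logMAR acuity but does not say which of the four acuity measures it concerns.

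**The concern.** The Statement of Problem (section C.a) sets out to check manufacturers' claims by "comparing symptoms and visual performance of two novel stenfilcon A lens designs". A test of a claim needs one agreed comparison that decides it. Here every measure has equal standing and each would presumably be tested at 5%, the only level the documents mention. A significant difference on any one measure could therefore be presented as the primary result, and a mixed set of results has no agreed reading. Once the data are unmasked, analysis cannot restore a choice that was not made beforehand. The freedom is widened by the unstated summaries of the defocus curve, the range of clear vision and objective accommodation.

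**Working it through.** **The plan's own figures.** The only error rate stated is the two-sided 0.05 in the sample-size paragraph (0.1 logMAR difference, SD 0.06, 80% power, fewer than 27 subjects, 30 enrolled for 10% dropout). The dropout step reproduces: 27/(1 − 0.10) = 30. The 27 does not. A paired t-test on those inputs needs 6 subjects if 0.06 is the SD of the paired difference, or 8 if it is the SD of a single measurement with uncorrelated periods (0.06 × √2 = 0.085). That is a separate matter. What counts here is that 0.05 is planned for a single acuity test, with no allowance for several.

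**Counting the tests.** The documents give no count, so it depends on the reading:

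- Defocus powers: (3.00 − (−3.00))/0.50 + 1 = 13.
- Section C.b list, curve reduced to one summary: CVS-Q 1 + acuity 4 + defocus 1 + objective 1 = 7.
- Protocol list, range of clear vision as one value: 7 + 1 = 8.
- Protocol list, far and near blur points separate: 7 + 2 = 9.
- As the last, with every defocus power tested: 1 + 4 + 2 + 13 + 1 = 21.

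Objective accommodation may yield more than one value, and the CVS-Q correlations are extra, so 21 is not a ceiling.

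**Chance of at least one p<0.05 if the lenses do not differ.** For k independent tests it is 1 − 0.95^k:

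- k = 7: 1 − 0.698 = 0.302
- k = 8: 1 − 0.663 = 0.337
- k = 9: 1 − 0.630 = 0.370
- k = 21: 1 − 0.341 = 0.659

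For tests with a common correlation ρ, which is an assumption because the documents give none, it is

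1 − ∫ φ(u) [Φ((1.96 − √ρ·u)/√(1−ρ)) − Φ((−1.96 − √ρ·u)/√(1−ρ))]^k du.

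| Tests | ρ = 0 | ρ = 0.3 | ρ = 0.5 | ρ = 0.7 | ρ = 0.9 |
|---|---|---|---|---|---|
| 7 | 30% | 27% | 23% | 18% | 11% |
| 8 | 34% | 30% | 25% | 19% | 12% |
| 9 | 37% | 33% | 27% | 20% | 12% |
| 21 | 66% | 55% | 43% | 30% | 16% |

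With independent tests the chance passes one half at 14 (1 − 0.95^14 = 0.512). Even one test for each of the five protocol bullets gives 1 − 0.95^5 = 0.226.

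**What adjustment would cost.** With 27 evaluable subjects and a two-sided paired t-test, the difference detectable at 80% power, in units of the SD of the paired difference, is:

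- one primary at 0.05: 0.56 SD;
- Bonferroni over 7 (0.05/7 = 0.0071): 0.73 SD;
- Bonferroni over 9 (0.05/9 = 0.0056): 0.75 SD;
- Bonferroni over 21 (0.05/21 = 0.0024): 0.82 SD.

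**The case against.** Several points on the other side are sound.

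*The count is an inference.* A reader might infer that the plan commits to at least 9 and at most 21 tests. The documents support neither bound. Range of clear vision may be one value, the section C.b list omits it, nothing says each defocus power will be tested, and objective accommodation has no stated number of parameters.

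*A false positive is not shown to be likely.* A reader might infer that a chance finding is more probable than not. Among the cases in the table, that holds only for 21 tests with little correlation (66% at ρ = 0, 55% at 0.3). Little correlation is implausible there: neighbouring defocus steps are measured in the same eyes at the same visit, and the zero-defocus point overlaps distance acuity.

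*The aim does not clearly shift.* A reader might set the accommodative burden named in Background and Rationale against the wording "efficacy of novel lenses like Biofinity Energys and MyDay Energys in alleviating CVS". The latter comes from a relevance statement in a funding application and is not an objective. Symptoms and visual performance can be read as the means of measuring the protocol's aim.

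*One primary may have been intended.* The publication plan uses the singular and the sample size uses acuity. That may be so, but acuity has four versions and no text connects either clue to a named endpoint.

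*The study is small and never calls itself confirmatory.* On the acuity inputs, Bonferroni over 21 tests still leaves over 99% power with 27 evaluable. This shows that control would be affordable for acuity. It does not supply the control, and the documents give no SD for the other measures.

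These points limit the size of the claim. They leave the core: all measures are primary, none is ranked, and nothing is adjusted.

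**Conclusion.** The concern holds in this form: the plan has roughly 7 to 21 or more unranked, unadjusted primary comparisons and no identifiable confirmatory test. If the lenses do not differ, the chance of at least one nominally significant result is about 30% to 66% under independence, 23% to 43% at correlation 0.5 and 18% to 30% at 0.7. Those figures assume each comparison is tested at two-sided 5% with equal correlation between tests. Both the correlations and the test counts are assumptions, since the documents state neither. Across the correlations from 0 to 0.7, the rate is between about three and a half and thirteen times the nominal 5%. This is more than a missing detail, because following the text as written produces the inflation.

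**What to change.** In the protocol's Experimental design and Statistical Analysis text, and in section C.b of the research plan, name one primary endpoint before unmasking. Test it lens against lens within subject at two-sided 5%.

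CVS-Q total score at the end of each wear period is one defensible choice: it is the eligibility measure and the anchor for the planned correlations. It is not the only one. Its frequency scale is worded in weekly terms, while wear may be as short as five days. One named acuity measure or one named accommodation measure would cure the defect equally well.

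Make all other measures secondary. Pre-specify one defocus-curve summary per subject and lens, for example area under the curve, and likewise state the values to be used for range of clear vision and objective accommodation. Test the secondaries with Holm adjustment, or report them as estimates with 95% confidence intervals only. If Holm is used, say whether the secondaries are tested only after a significant primary. Without that gate, the overall bound is 0.05 + 0.05 = 0.10.

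The cost is more than wording. Secondary measures face a stricter threshold, and the sample-size statement must be rewritten for the named endpoint. With 27 evaluable, 80% power corresponds to about 0.56 SD of the paired difference. The documents give neither an SD nor a meaningful difference for the CVS-Q, so if it is chosen, both must be found and justified.

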### *Inclusion criteria:*

- Score of >6 on CVS-Q
- Male or female
- Age >18 years to 35 years of age
- Experienced, well-adapted contact lens wearers
- Spherical equivalent refractive error between  $\pm 6.00$ DS with astigmatism < -0.75D
- Normal stereopsis and binocular status

### *Exclusion criteria:*

- Monovision
- History of refractive surgery
- Binocular vision abnormalities
- Current ocular or systemic disease that may affect the eye
- Allergic reactions of ocular surfaces or adnexa that may be induced or exaggerated by wearing contact lenses or use of contact lens solutions.

- If eyes become red or irritated.
- The patient is unable to follow lens care regimen or unable to obtain assistance to do so

*Sample size:*

Sample size calculations were based on logMAR visual acuity values from Elliott et al. (1995). Assuming a clinically significant difference of 0.1 logMAR and a standard deviation of 0.06, a two-tailed t-test with  $\alpha=0.05$  and  $\beta=0.20$  indicates a sample size of <27 subjects. To account for a 10% dropout rate, 30 subjects will be enrolled.

*Statistical Analysis:*

Descriptive statistics will be provided for the cohort including age, gender, equivalent spherical refraction, hours spent using a smart device per day, and average wearing time per day. Primary outcome measures will be compared using either parametric or non-parametric testing after testing sample distributions for normalcy. Correlations between CVS-Q and outcome measures will be assessed.

This study will comply with the tenets of the Helsinki Declarations and will be approved by the Institutional Review Board.

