Sample size calculations were based on logMAR visual acuity values from Elliott et al. (1995). Assuming a clinically significant difference of 0.1 logMAR and a standard deviation of 0.06, a two-tailed t-test with  $\alpha=0.05$  and  $\beta=0.20$  indicates a sample size of <27 subjects. To account for a 10% dropout rate, 30 subjects will be enrolled.

*Statistical Analysis:*

Descriptive statistics will be provided for the cohort including age, gender, equivalent spherical refraction, hours spent using a smart device per day, and average wearing time per day. Primary outcome measures will be compared using either parametric or non-parametric testing after testing sample distributions for normalcy. Correlations between CVS-Q and outcome measures will be assessed.

This study will comply with the tenets of the Helsinki Declarations and will be approved by the Institutional Review Board.

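### The sample size of <27 does not follow from its stated inputs, which need 6 to 8 pairs, and the other listed primary outcomes have no power basis

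*Combined protocol and SAP*

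**What the plan says.** The sample size paragraph appears after the exclusion criteria in the protocol and again in section C.b (Experimental design) of the research plan. Acuity is the only basis: "Sample size calculations were based on logMAR visual acuity values" taken from a 1995 study. The inputs are given as "Assuming a clinically significant difference of 0.1 logMAR and a standard deviation of 0.06", with a "two-tailed t-test", alpha 0.05 and beta 0.20. The result is that this "indicates a sample size of <27 subjects. To account for a 10% dropout rate, 30 subjects will be enrolled". The paragraph does not say whether the test is paired, or whether 0.06 is the SD of single measurements or of within-subject differences.

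The Experimental design section describes a two-lens crossover. Under a single heading of primary outcome measures it lists CVS-Q, high- and low-contrast acuity, range of clear vision (protocol version only), and subjective and objective accommodation. None is ranked above the others. Entry requires a "Score of >6 on CVS-Q", and the background gives the purpose as comparing the lenses in "alleviating accommodative burden associated with digital device usage". The Statistical Analysis paragraph allows parametric or non-parametric tests, depending on a normality check.

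**The concern.** A difference of 0.1 with an SD of 0.06 is a standardised effect of 1.67, which is very large. A within-subject comparison of an effect that size needs only a handful of subjects, so 27 looks far too big to have come from these inputs. An upper bound is also not what a sample size calculation returns.

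Two things are at stake. First, the only justification offered for N=30 cannot be reproduced, which an ethics board, funder or journal may notice. Second, the calculation covers one of several listed primary outcomes. Subjects are selected on symptoms, and the stated purpose concerns symptoms and accommodation, yet the plan says nothing about what difference it could detect on either.

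**Working it through.** **Inputs from the plan:** difference 0.1 logMAR; SD 0.06; two-sided alpha 0.05; power 0.80; dropout 10%; crossover design.

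**Dropout step.** 27 / (1 − 0.10) = 30. This reproduces, so 27 is the number that was carried into enrolment.

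**Base number.** Power is taken from the noncentral t distribution. For n pairs, df = n − 1 and noncentrality = (difference / SD of difference) × √n. For two groups of n, df = 2n − 2 and noncentrality = (difference / SD) × √(n/2). If 0.06 is the per-lens SD and r the within-subject correlation, the SD of the difference is 0.06 × √(2(1 − r)). That is 0.0849 at r = 0 and 0.06 at r = 0.5.

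| Reading of the inputs | Standardised effect | Power just below | Power at required n | Required |
|---|---|---|---|---|
| Paired, SD of difference 0.06 | 0.1/0.06 = 1.67 | n=5: 0.793 | n=6: 0.899 | 6 |
| Paired, per-lens SD 0.06, r = 0 | 0.1/0.0849 = 1.18 | n=7: 0.739 | n=8: 0.815 | 8 |
| Two parallel groups, SD 0.06 | 1.67 | 6 per group: 0.740 | 7 per group: 0.816 | 14 in total |

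The normal approximation gives smaller paired numbers still, 3 and 6.

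**Could an unstated choice explain 27?** On the two paired readings, 90% power needs 7 to 10 pairs and 95% power needs 7 to 12. A Bonferroni correction over 20 tests needs 10 to 16 pairs. With parallel groups, that correction gives 14 per group (28 in total), but neither the correction nor that design is in the plan. For 27 pairs to be the 80% answer at 0.1 logMAR, the SD of the difference would have to be 0.1/0.560 = 0.179, about three times 0.06.

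**What 27 completers give.**
- Power for 0.1 logMAR is above 99.9% on both paired readings.
- The difference detectable with 80% power by a paired t-test is 0.560 SD of the within-subject difference, for any paired outcome.
- For acuity this is 0.560 × 0.06 = 0.034 logMAR, or 0.560 × 0.0849 = 0.048 logMAR.
- If a rank test is used and its efficiency is assumed to be 0.864, the effective number is 27 × 0.864 = 23.3 and the detectable difference is about 0.61 SD.
- The documents give no SD for CVS-Q. If the SD of the within-subject difference is assumed to be 3, 4 or 5 points, 0.560 SD is 1.7, 2.2 or 2.8 points.

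**The case against.** The strongest reply is that nothing false is claimed. The plan writes "indicates a sample size of <27 subjects", and 6 or 8 is below 27. The power promised for the one stated effect is met with a wide margin. Acuity is itself a listed primary outcome, and visual performance is part of the stated aim, so sizing on it is legitimate. Enrolment does not change.

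Most of this stands. The error is in the safe direction for acuity, and sizing on acuity is incomplete rather than wrong. The inequality does not rescue the paragraph, though: 27 is the figure divided by 0.9 to reach 30, so it served as the result, and the inputs do not yield it.

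A reader might infer more than the documents support:
- *That the trial falls short of 80% power.* For the only effect stated, it exceeds 99.9%.
- *That 30 is too few for symptoms.* With no CVS-Q difference or SD given, adequacy is unknown in either direction.
- *That a null CVS-Q result could not be interpreted.* A confidence interval for the between-lens difference would interpret it, whatever the planning calculation was.
- *That the plan regards acuity differences under 0.1 logMAR as unimportant.* It calls 0.1 clinically significant and says nothing about smaller differences.

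**Conclusion.** Wrong as written; should be fixed. The stated inputs need 6 or 8 pairs, or 14 subjects in parallel groups, and not the 27 that led to 30. The range 6 to 8 depends on which SD 0.06 is, with zero correlation as the assumption behind 8; a positive correlation would lower it. The consequence is limited: acuity is more than covered, and N=30 need not change. What is missing is a valid derivation of N and any power basis for CVS-Q and the accommodation measures. The 0.56 SD figure rests on 27 completers and a paired t-test, the 0.61 SD figure on an assumed rank-test efficiency of 0.864, and the CVS-Q points on assumed SDs.

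**What to change.** Keep N=30 and rewrite the paragraph in both places:
- Delete <27, name the test as paired, and say whether 0.06 is the per-lens SD or the SD of the within-subject difference.
- State that 30 enrolled with 10% dropout leaves 27 completers, who give 80% power at two-sided 5% for a between-lens difference of 0.56 SD of the within-subject difference (about 0.61 SD for a rank test, assuming efficiency 0.864). Apply this to every paired primary outcome, including CVS-Q and accommodation.
- For acuity, give the detectable difference as 0.034 or 0.048 logMAR, according to which SD 0.06 is.
- Express the CVS-Q figure in points only with a sourced SD, preferably beside a difference judged meaningful. Otherwise label 1.7, 2.2 or 2.8 points as assuming an SD of 3, 4 or 5.
- Say that N was fixed in advance and that these are detectable differences, since a figure worked back from N does not justify N.

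Do not use this paragraph to rank the outcomes. The plan ranks none, and choosing a single primary outcome is a separate decision.

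The cost is one paragraph in two places, with no change to enrolment or conduct. The stated case for N will look less generous than it does on acuity alone.
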